5.2.1. Analyses for Continuous Endpoints

Unless otherwise stated, continuous variables will be presented using summary statistics: number of observations, arithmetic mean, standard deviation, median, minimum and maximum values.

Geometric mean and geometric cv% will also be presented for continuous variables using ln analysis scale.

5.2.2. Analyses for Categorical Endpoints

Categorical variables will be presented using summary statistics: number of observations and percentages.

5.2.3. Mixed Effect Model

A mixed effects model with treatment as a fixed effect and participant as a random effect will be used for the analysis of food effect on PF-07296893 PK endpoints.

Estimates of the adjusted (least squares) mean differences (Test-reference) and corresponding 90% confidence intervals (CIs) will be obtained from the model. The adjusted mean differences and 90% CIs for the differences will be exponentiated to provide estimates of the ratio of adjusted geometric means (Test/Reference) and 90% CIs for the ratios.

The mixed effects model will be implemented using SAS Proc Mixed, with REML estimation method and the Kenward-Roger degrees of freedom algorithm.

Residuals from the models will be examined for normality and the presence of outliers via visual inspection of plots of residuals vs predicted values and normal probability plots of residuals, but these will not be included in the clinical study report. If there are major deviations from normality or outliers (where studentized [conditional] residuals are greater than 3 or less than -3), then the effect of these on the conclusions may be investigated through alternative transformations and/or analyses excluding outliers. Justification for any alternative to the planned analysis will be given in the report of the study if applicable.

Example SAS code is provided in [Appendix 2](#).

5.3. Methods to Manage Missing Data

5.3.1. Missing Safety Data

For the analysis of safety endpoints, the sponsor data standard rules for imputation will be applied.

5.3.2. Missing PK Concentration Data

In all PK data presentations (except listings), concentrations below the limit of quantification (BLQ) will be set to zero. In listings, BLQ values will be reported as “<LLOQ”, where LLOQ will be replaced with the value for the lower limit of quantification (LLOQ).

In PK summary tables and plots of mean/median profiles, statistics will be calculated having set concentrations to missing if one of the following cases is true:

1. A concentration has been collected as ND (ie not done) or NS (ie no sample),
2. A deviation in sampling time is of sufficient concern or a concentration has been flagged anomalous by the pharmacokineticist/statistician.

Note that summary statistics will not be presented at a particular timepoint if more than 50% of the data are missing.

Participants who experience events that may affect their PK profile (e.g., lack of compliance with dosing or vomiting) may be excluded from the PK analysis. At the discretion of the pharmacokineticist, a concentration value may also be excluded if the deviation in sampling time is of sufficient concern or if the concentration is anomalous for any other reason.

A full list of protocol deviations will be compiled and reviewed to identify major and minor deviations prior to database closure.

5.3.3. Missing Plasma PK Parameters

Actual PK sampling times will be used in the derivation of plasma PK parameters.

If a PK parameter cannot be derived from a participant's concentration data, the parameter will be coded as NC (ie not calculated). (Note that NC values will not be generated beyond the day that a participant discontinues).

In summary tables, statistics will be calculated by setting NC values to missing; and statistics will be presented for a particular dose with ≥ 3 evaluable measurements. For statistical analyses (i.e. mixed effects model), PK parameters coded as NC will also be set to missing; and analyses will not be performed for a particular parameter if more than 50% of the data are NC.

If an individual participant has a known biased estimate of a PK parameter (due for example to an unexpected event such as vomiting before all the compound is adequately absorbed in the body), this will be footnoted in summary tables and may not be included in the calculation of summary statistics or statistical analyses.

6. ANALYSES AND SUMMARIES

6.1. Primary Endpoint(s)

For all presentations, study day will refer to the day within a particular treatment period, unless otherwise specified.

6.1.1. Adverse Events

Adverse events will be listed and summarized by dose and treatment (if applicable) and overall, in accordance with sponsor reporting standards using the safety analysis set defined in Section 4.

The AEs will be presented sorted in descending frequency based on the overall number of AEs (by preferred term or system order class as appropriate) across treatments.

6.1.2. Clinical Safety Laboratory Tests

Safety laboratory data will be listed and summarized by dose and treatment (if applicable) and overall, in accordance with the sponsor reporting standards using the safety analysis set defined in Section 4. Baseline is as defined in Section 3.1.2.

Data collected at screening that are used for inclusion/exclusion criteria, will be considered source data, and will not be required to be reported, unless otherwise noted.

In summary and listing tables, laboratory abnormalities occurring pre-dose on Day -1 for each period starting with Period 2, will be attributed to the treatment from the previous period (eg, for Cohort 1, an occurrence pre-dose at Period 2 Day -1 will be attributed to the Period 1 dose).

6.1.3. Vital Signs

Absolute values and CFB in supine systolic and diastolic BP, pulse rate, temperature and respiratory rate will be listed and summarized by dose and treatment and timepoint, according to sponsor reporting standards, using the safety analysis set defined in Section 4. Baseline is as defined in Section 3.1.3.

Mean absolute values and CFB for supine systolic and diastolic BP, pulse rate, temperature, and respiratory rate will be plotted against time point. On each plot there will be one line for each treatment with all treatments on the same plot. Corresponding individual plots of changes from baseline will also be produced for each treatment.

Maximum increase and decrease from baseline over all measurements taken post-dose for supine systolic and diastolic BPs, pulse rate, temperature and respiratory rate will be summarized by treatment, according to sponsor reporting standards.

Minimum and/or maximum absolute values and CFB for supine vital signs will also be summarized descriptively by treatment using categories as defined in Appendix 1. Numbers and percentages of participants meeting the categorical criteria will be provided. All planned and unplanned post-dose time points will be counted in these categorical summaries. All values meeting the criteria of potential clinical concern will be listed.

Values meeting the categorical criteria occurring pre-dose on Day 1 for each period starting with Period 2, will be attributed to the treatment from the previous period (e.g., for Cohort 1, an occurrence pre-dose at Period 2 Day 1 will be attributed to the Period 1 dose).

Data collected at screening that are used for inclusion/exclusion criteria, will be considered source data, and will not be required to be reported, unless otherwise noted.

6.1.4. Continuous Cardiac Monitoring

Data will be reviewed and summarized on an ongoing basis during the study to evaluate the safety of participants.

All abnormal rhythms will be recorded and reviewed by the investigator for the presence of rhythms of potential clinical concern. The time, duration, and description of the clinically significant event will be recorded in the CRF. Events deemed of clinical concern will be recorded as AEs and will be summarized as part of the standard AE outputs.

6.1.5. 12-Lead ECG

Absolute values and CFB in QT, heart rate, QTcF, PR and QRS will be summarized by dose and treatment and timepoint using sponsor reporting standards, using the safety analysis set defined in Section 4. Baseline is as defined in Section 3.1.5.

Mean CFB in QT, heart rate and QTcF will be plotted against time post-dose. On each plot there will be one line for each treatment. Corresponding individual plots of CFB will also be produced for each treatment.

Changes from baseline in QTcF will also be plotted separately against drug concentrations of PF-07293893. This will be a scatter plot for all observations where QTcF and drug concentration are recorded. Placebo data will also be included (with drug concentration set to zero). Different symbols will be used for each treatment.

Maximum increase from baseline for QTcF, heart rate, PR and QRS values will be summarized by dose and treatment, according to sponsor reporting standards.

ECG endpoints and CFB (QTcF, PR and QRS) will also be summarized descriptively by dose and treatment using categories as defined in Appendix 1. Numbers and percentages of participants meeting the categorical criteria will be provided. All planned and unplanned postdose time points will be counted in these categorical summaries.

Values meeting the categorical criteria occurring pre-dose on Day 1 for each period starting with Period 2, will be attributed to the treatment from the previous period (e.g., for cohort 1, an occurrence pre-dose at Period 2 Day 1 will be attributed to the Period 1 dose).

Listings of participants with any single post-dose value >500 msec will also be produced for QTcF.

Data collected at screening that are used for inclusion/exclusion criteria, will be considered source data, and will not be required to be reported, unless otherwise noted.

6.1.6. Physical Examinations

Physical examination findings collected during the study will be considered source record and will not be required to be reported, unless otherwise noted. Any untoward physical examination findings that are identified during the active collection period and meet the definition of an AE or SAE will be recorded as AEs or SAEs and will be summarized as part of the standard AE outputs.

Data collected at screening that are used for inclusion/exclusion criteria, will be considered source data, and will not be required to be reported, unless otherwise noted.

6.1.7. Neurological Examinations

Neurological examination data collected during the course of the study will be considered source data and will not be required to be reported, unless otherwise noted. Any untoward neurological examination findings that are identified during the active collection period and meet the definition of an AE or SAE will be recorded as AEs or SAEs and will be summarized as part of the standard AE outputs.

6.2. Secondary Endpoint(s)

The PK parameters detailed in Section 3.2 will be listed and summarized for participants in the PK Parameter Analysis Set (as defined in Section 4). Missing values will be handled as detailed in Section 5.3.2 and 5.3.3. Each PK parameter will be summarized by dose (and formulation and fasting condition, if appropriate) as applicable. Each summary will include the set of summary statistics as specified in Table 4.

Table 4. Summary Statistics for PF-07293893 Plasma PK Parameters

Parameter	Summary Statistics
AUC _{last} , AUC _{inf} [*] , C _{max} ,	N, arithmetic mean, median, cv%, standard deviation, minimum, maximum, geometric mean and geometric cv%.
T _{max}	N, median, minimum, maximum
t _{1/2} [*]	N, arithmetic mean, median, cv%, standard deviation, minimum, maximum.

*If data permit

Supporting data from the estimation of t_{1/2} will be listed by treatment and dose where applicable: terminal phase rate constant (k_{el}); goodness of fit statistic from the log-linear regression (r²); the percent of AUC_{inf} based on extrapolation (AUC_{extrap}%); and the first, last, and number of time points used in the estimation of k_{el}. These data may be included in the CSR.

PF-07293893 concentrations will be presented using participants in the PK Concentration Set (as defined in Section 4) and will include:

- a listing of all concentrations sorted by participant ID, dose and treatment (if applicable) and nominal time post-dose. The concentration listing will also include the actual times. Deviations from the nominal time will be given in a separate listing.
- a summary of concentrations by dose and treatment (if applicable) and nominal time post-dose, where the set of statistics will include n, mean, median, standard deviation, coefficient of variation (cv), minimum, maximum and the number of concentrations above the lower limit of quantification.

- individual concentration-time plots by dose (on both linear and semi-log scales) and treatment (if applicable) against actual time post-dose (there will be separate spaghetti plots for each dose and treatment [if applicable] per scale).
- individual concentration-time plots by participant (on both linear and semi-log scales) against actual time post-dose (there will be separate spaghetti plots for each dose and treatment [if applicable] per scale).
- median concentration-time plots (on both linear and semi-log scales) against nominal time post-dose by dose (all doses on the same plot per scale, based on the summary of concentrations by dose and time post-dose) and treatment (if applicable).
- mean concentration-time plots (on both linear and semi-log scales) against nominal time post-dose by dose (all doses on the same plot per scale, based on the summary of concentrations by dose and time post-dose) and treatment (if applicable).

The scale used for the x-axis (time) of these plots will be decided on review of the data, and will depend on how long PF-07293893 concentration is quantifiable in the matrix.

For summary statistics, median and mean plots by sampling time, the nominal PK sampling time will be used. For individual participant plots by time, the actual PK sampling time will be used.

To assess any food effect in SDD formulation as a tertiary objective, a mixed effects model will be performed separately on the natural log transformed AUC_{inf} , AUC_{last} , and C_{max} with fasting condition included as a fixed effect and participant as a random effect as described in Section 5.2.3. Only data from the respective periods in the cohort 3 will be included. The fasted state will be the reference and the fed state will be the test treatment.

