Days Relative to Day 1	Day -28 to Day -2									
 All screening should be done \leq28 days before the first dose. Day relative to start of study intervention (Day 1). Day 1 activities at time=0 hours are prior to the dose, except for study intervention administration. On-site follow-up visit to occur on Day 8±1 after the final dose of study intervention. Follow-up may occur via telephone contact and must occur 28 to 35 days after administration of the final dose of study intervention.
Hours After Dose		0	24	36	48	72				
Continuous cardiac telemetry		X								
 Baseline telemetry to be recorded for at least 2 hours prior to the first dose in Period 1 only. This may be done immediately prior to dosing or at some 2-hour continuous interval in the 24 hours prior to dosing, as long as the participant is awake. Post-dose telemetry will continue for 8 hours after dosing. See Section 8.3.4.1 for additional information.
Supine BP	X			X	X	X	X		X	
 Single supine blood pressure at screening, follow-up visit and ET. Triplicate measures of supine blood pressure at all other times. See Section 8.3.3 for additional information.
Temperature, pulse rate and respiratory rate				X		X				
 See Section 8.3.3 for additional information.
Study intervention administration										
 Participants should fast for at least 10 hours prior to dosing, except for periods in which food effects are investigated. Dosing under fasted or fed conditions is to occur as outlined in Section 5.3.2.
Standardized meal/snack		X	X	X	X	X				
 See Section 5.3.2 for detailed instruction.
Blood samples for:										
Safety laboratory	X	X		X			X	X	X	
 Participant should fast for at least 4 hours prior to sample collection. Safety laboratory includes hematology, chemistry, and urinalysis, which are listed in Appendix 2.
FSH	X									
 For confirmation of postmenopausal status only in females <60 years old and not using hormonal or HRT only.
HIV, HBsAg, HBsAb, HBcAb, HCVAb	X									
 See Appendix 2: Clinical Laboratory Tests.

Table 1. Study Schedule of Assessment

Visit Identifier Abbreviations used in this table may be found in Appendix 10 .	Screen	Period 1 to Period 4					F/U		ET	Notes

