6.1.1. Administration

For fasted period(s):

- Following an overnight fast of at least 10 hours, participants will receive study intervention at approximately 08:00 hours (plus or minus 2 hours) without breakfast on Day 1.

For fed period(s):

- Following an overnight fast of at least 10 hours, participants will receive breakfast approximately 30 minutes prior to dosing on Day 1 which is to be completed within approximately 20 minutes as outlined in [Section 5.3.2](#). The participants will then receive study intervention approximately 10 minutes after completion of the meal at approximately 08:00 hours (plus or minus 2 hours).

For all periods, investigator site personnel will administer a single oral dose of study intervention on Day 1 of each period with ambient temperature water to a total volume of approximately 240 mL. Administer study intervention according to the EDR.

Administration of study intervention(s) at the site will be performed by an appropriately qualified and trained member of the study staff as allowed by local, state, and institutional guidance.

Following administration of study intervention(s) at the site, participants will be observed by an appropriately qualified and trained member of the study staff. Appropriate medication and other supportive measures for management of a medical emergency will be available in accordance with local guidelines and institutional guidelines.

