2.3. Study Design

This is a randomized, investigator- and participant-blind, sponsor-open, placebo-controlled, first-in-human, single ascending oral dose, 4-period, crossover study of PF-07293893 administered to healthy adult participants. Approximately 24 healthy adult participants (up to 3 cohorts of approximately 8 participants each) will be enrolled in this study. The first 2 cohorts are planned, and the third cohort is optional. In each period, participants will be randomized to either PF-07293893 or placebo in a ratio of 3:1. Each participant is planned to undergo up to 4 treatment periods receiving up to 4 doses of PF-07293893 and up to 2 doses of placebo.

Precautionary sentinel dosing will be used in any period evaluating escalating doses of PF-07293893 and may be omitted for periods when repeating a dose level or administering a lower dose level than previously evaluated. For periods with sentinel dosing, two participants (1 receiving PF-07293893 and 1 receiving placebo) will be dosed initially before the remaining participants of that period are dosed. Safety and tolerability data through at least 24 hours post-dose for the sentinel participants will be reviewed prior to dosing the remaining participants of that period.

The study design schema is shown below in Figure 1.

Figure 1. Study Design Schema^{a,b,c}

- a. Doses shown for each cohort except the starting dose in Cohort 1 are planned doses and may be modified based on emerging data from previous cohorts. Similarly, assignment to study intervention may be modified. n represents number of participants.
- b. SDD extemporaneous prep will be used for dose escalation in this study. PK for crystalline formulation (fasted/fed) may be studied in remaining periods of Cohort 2 and/or optional Cohort 3 when it becomes available.
- c. Precautionary sentinel dosing will be used in any period evaluating escalating doses of PF-07293893. For such periods, 2 participants (1 receiving PF-07293893 and 1 receiving placebo) will be dosed initially before the remaining participants of that period are dosed. Safety and tolerability data through at least 24 hours post-dose for the sentinel participants will be reviewed prior to dosing the remaining participants of that period. Sentinel dosing may be omitted when repeating a dose level or administering a lower dose level than previously evaluated.

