5.2. General Methods

Unless otherwise stated, all summaries and plots will be presented by dose and treatment. Each formulation of PF-07293893 administered during the study and fasting status will be considered as separate treatments. If a dose level is repeated across 2 or more cohorts, the data will be combined, unless the dose is in a different formulation or food state, in which case the dose would be reported separately.

Unless otherwise stated, the summary tables and/or statistical analyses will only include a single pooled placebo group across all included cohorts with SDD formulation. Placebo will be pooled from all dose escalation periods but not for the fed period (if conducted) nor for crystalline formulation period (if conducted).

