Appendix 2. Example SAS Code for Statistical Analyses

```
proc mixed data = dataset;
  class subjid trt;
  model &var = trt /residual ddfm = kr;
  random subjid;
  lsmeans trt / diff cl alpha = 0.1;
run;
```

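### The food-effect models have no period term and the documents do not state the fed/fasted order, so food and period may not be separable in the fed/fasted ratio

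*SAP*

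**What the plan says.** **Model.** SAP 5.2.3 sets the general form: "A mixed effects model with treatment as a fixed effect and participant as a random effect will be used for the analysis of food effect". SAP 6.2 applies it to the SDD formulation "with fasting condition included as a fixed effect and participant as a random effect", with fasted as reference and fed as test, and SAP 6.3.2 uses the same structure for the crystalline form. The code in SAP Appendix 2 agrees: "model &var = trt /residual ddfm = kr", with only participant and treatment as class variables. No period or sequence term appears in any of these places. The output is a ratio of adjusted geometric means with a 90% CI.

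**Data.** For the SDD comparison, SAP 6.2 states: "Only data from the respective periods in the cohort 3 will be included".

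**How fed state is assigned.** The wording goes by period. The placebo-pooling rule in SAP 5.2 reads: "Placebo will be pooled from all dose escalation periods but not for the fed period (if conducted". The notes to the Schedule of Activities (Protocol 1.3) say: "Participants should fast for at least 10 hours prior to dosing, except for periods in which food effects are investigated". Protocol 6.1.1 gives separate dosing instructions for fasted and for fed periods.

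**What is randomised.** SAP 2.3 (and Protocol 4.1) says: "In each period, participants will be randomized to either PF-07293893 or placebo in a ratio of 3:1". Protocol 6.3 refers to a randomisation schedule but mentions no fed/fasted sequence.

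**Room to adapt.** Protocol 9.3.2.2 names the same mixed model and allows the SAP to alter it to suit the dosing scheme. SAP version 2 was issued to add the SDD food effect; SAP 2.1 records no change from the protocol's analysis plan.

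**The concern.** A fed/fasted comparison within participants sets one period against another. Anything else that differs between those periods, such as assay batch, suspension preparation or time in confinement, acts as a period effect. How far it reaches the ratio depends on two things the reader needs to know: the order in which participants met the two conditions, and whether the model accounts for period. The model does not, and the order is not stated.

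At stake are the fed/fasted ratios for AUCinf, AUClast and Cmax and their 90% CIs. If the two conditions were run in one common order, each ratio would carry any period shift in full, and the interval would give no sign of it.

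**Working it through.** The documents give no sample size, power or precision figure for the food-effect comparison, so there is no figure of theirs to reproduce.

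**Inputs from the documents**
- About 8 participants per cohort at 3:1, hence 8 × 3/4 = 6 active and 2 placebo per period (Protocol 4.2).
- Treatment fixed, participant random, log scale, 90% CI (SAP 5.2.3).

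**Assumptions not in the documents**
- No true food effect (true ratio 1.00).
- Period shift of 1.10 or 1.20.
- Within-participant CV of 15–35%.
- 6 complete pairs. Placebo allocation could leave fewer, so 4 is also shown.

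**1. Common order.** Fed is then the same column as second (or first) period. The planned model's expected log ratio is food + δ, where δ is the log period shift. With no food effect, a shift of 1.10 gives 1.100 and a shift of 1.20 gives 1.200, whether 6, 5 or 4 participants are active in both periods. A REML simulation (400 runs per setting, within-CV 25%, between-CV 40%) agrees within simulation error: for a 1.20 shift it returned 1.189 with 6 in common and 1.193 with 4 (Monte Carlo SE about 0.7–0.8% on the log scale). Adding period leaves a fixed-effects matrix of rank 2 with 3 columns, so food is no longer estimable.

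**2. Mixed, unbalanced order.** With 4 participants in one order and 2 in the other, the bias is δ × (4 − 2)/6 = δ/3. For a 1.20 shift that is 1.20^(1/3) = 1.063; for 1.10 it is 1.10^(1/3) = 1.032. With period in the model, both return 1.000.

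**3. Balanced order (3:3).** The bias is δ × (3 − 3)/6 = 0, with or without the term. Without it, the expected variance of the paired differences rises from 2σ² to 2σ² + (6/5)δ², where σ² = ln(1 + CV²). At CV 20% and a 1.20 shift:
- 2σ² = 2 × ln(1.04) = 0.0784.
- (6/5)δ² = 1.2 × 0.1823² = 0.0399.
- The standard error grows by about √(0.1183/0.0784) = 1.23.

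The term itself takes one residual degree of freedom, 5 to 4, which moves the 90% CI multiplier from 2.015 to 2.132 (factor 1.06).

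**4. Coverage under a common order.** SE = σ√(2/n), the non-centrality is δ/SE, and coverage is the non-central t probability between ±t(0.95, n − 1). Example at n = 6, CV 20%: σ = 0.198 and SE = 0.198 × √(2/6) = 0.114. A 1.10 shift gives non-centrality 0.0953/0.1143 = 0.834 and coverage 0.813.

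| Pairs | Within-CV | 10% shift | 20% shift |
|---|---|---|---|
| 6 | 15% | 0.749 | 0.429 |
| 6 | 20% | 0.813 | 0.604 |
| 6 | 25% | 0.843 | 0.700 |
| 6 | 30% | 0.860 | 0.757 |
| 6 | 35% | 0.870 | 0.792 |
| 4 | 20% | 0.851 | 0.730 |

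Nominal coverage is 0.90. With 6 pairs, a 5% shift leaves coverage at 0.86–0.89 across the same CV range.

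**The case against.** **The order is unknown.** The schema figure is not shown, and the administrative change letter that added the SDD food effect is not among the documents. SAP 6.2's reference to periods of Cohort 3 fits either a common or a mixed order. The mention of a single fed period in SAP 5.2 leans towards a common order without settling it. This objection stands. A reader might infer that any period shift will be reported as a food effect; the documents do not support that, because a balanced order would remove the bias.

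**The missing term is not always the fault.** Under a common order, leaving period out is the only way to fit the contrast at all, and under balanced order the term changes no point estimate. That also stands. Omission biases the ratio only when order is mixed and unbalanced; under a common order the limit lies in the design.

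**No period shift of this size is documented.** Correct. The plan has a washout of at least 7 days, standardised meals and activity, two-operator preparation and a validated assay. These reduce period effects, and the washout mainly limits carryover, but they do not rule out differences between periods.

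**The analysis is minor.** The food effect is tertiary, with no hypothesis test, decision rule or equivalence bound. A reader might take these ratios to be the study's only modelling, but Protocol 9.3.1.1 also plans concentration–QT modelling. Nor does the SAP depart from the protocol, which names the same model. All this limits the priority but does not remove the gap.

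**Conclusion.** The point holds conditionally. The absence of a period term and of any described randomisation of fed/fasted order is plain in the text. The effect on the ratio depends on an order the supplied text does not give: full transfer of a period shift under a common order, one third of it on the log scale under a 4:2 split, and none under balance, where the cost is a wider interval.

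The coverage loss, to about 75–87% for a 10% shift and 43–79% for a 20% shift, illustrates the common-order case only. It rests on assumed CVs, assumed shifts and 6 complete pairs, and it shrinks as variability rises. It is not a forecast for this trial. Because the analysis is tertiary and nothing is tested, this is an inexpensive improvement of modest priority.

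**What to change.** State the fed/fasted order in the SAP, then take the branch that applies.

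- **Order can still be set.** Where fed and fasted periods of the same formulation are compared, allocate participants to two balanced sequences, fed first and fasted first. Add period as a fixed effect in SAP 5.2.3, 6.2, 6.3.2 and Appendix 2 (`class subjid trt period; model &var = trt period`, options unchanged).
- **Common order, or dosing already complete.** Do not add the term. State in the SAP and the report that the ratio contrasts the fed period with the fasted period, and that food and period cannot be separated.

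The first branch costs one residual degree of freedom, a line in the randomisation schedule and two meal conditions run on the same dosing day. The second costs one sentence.
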